10.3 Other study parameters

Surgical complications

i.e., incidence of wound infections, wound breakdown, lymph oedema (see adverse effect Appendix 2) per patient and as absolute number. In relation to the previous

history and groin surgery performed, including all surgically treated patients (Groups non SLN cohort and A – C), comparing SLN treated groins with IFL treated groins.

Technical challenges

Description of unintended lesion of vena saphena magna, bleeding etc., duration of surgery to retrieve SLN. In relation to the previous history and groin surgery performed, including all surgically treated patients (Groups non SLN cohort and A – C), comparing SLN treated groins with IFL treated groins.

Patient's preferences

Standard treatment is uni- or bilateral IFL. In this study patients are offered SLN, with IFL when the SLN is not detected or retrieved. Preference for treatment is asked and noted in the file. The treating physician will note patients' preference in the application form. Patients will receive the Decisional Conflict Scale (DCS) and Decision Regret Scale (DRS). questionnaires regarding their treatment choices. (Group A – C) Decisions and regret scales will be compared between the groups (A – C) and related to patient characteristics like age, previous treatment and outcome like tumour positive groins and complications.

USS in follow up (Groups B1 - B2)

- 1) The number of suspicious USS in the follow up of women with negative LKT and SLN: USS with FNA, divided by the number of USS performed *100%.
- 2) Sensitivity and specificity of USS (with FNA) in women with negative LKT and SLN.
- 3) Protocol violation (USS not performed in women with negative LKT and SLN) divided by number of USS required in accordance with protocol *100%.

When a local or regional recurrence is diagnosed FU for this outcome stops.

Additional analyses

For the primary and secondary outcomes (failure of SLN and IFL procedure, feasibility, unexpected nodes, patients preferences, USS) univariate analyses will be done including the following parameters: tumour size, location, infiltration depth, treatment interval 1st and 2nd tumour, previous groin treatment, and age. Variables associated with ($P < 0.20$) in univariate analysis will be included in a multivariate logistic regression model. In the multivariate logistic and cox regression analyses, we only accepted ten events per variable to avoid overfitting (19).

The overall survival and progression free survival for the different groups (non SLN cohort and Groups A – C) will be described using the Kaplan-Meier analysis. The overall survival (OS) is defined as the interval between the date of surgery for 1st recurrent vulvar cancer and the date of death or last visit/date last known to be alive. Progression Free Survival (PFS) is defined as the interval between the date of surgery for 1st recurrent vulvar cancer and the date of documented disease progression, or last follow-up. Groin recurrence is censored in case of a 3rd local (vulvar) recurrence since any groin recurrence after such an event cannot be related to the 1st or 2nd recurrence. If a patient is lost to follow-up or dead because of unknown reason, she will be censored as of the date of last contact for the PFS.

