1. INTRODUCTION AND RATIONALE

The treatment for vulvar cancer has changed over the last decades. Currently the standard treatment for unifocal squamous cell carcinoma (SCC) of the vulva < 4 cm diameter without suspicious inguinofemoral lymph nodes at imaging consists of wide local excision and sentinel lymph node (SLN) procedure of the inguinofemoral lymph nodes (1-4). The advantages of SLN procedure over an inguinofemoral lymphadenectomy (IFL) are obvious: the short and long term sequels such as wound healing problems, lymph cyst formation, recurrent erysipelas and lymph oedema are much less common after SLN procedure (4). Lymphedema and recurrent erysipelas were seen in respectively 1.9% and 0.4% after SLN procedure and in respectively 25.2% and 16.2% after inguinofemoral lymphadenectomy (4). Groin recurrences after negative SLN procedures in primary vulvar SCC patients were reported in 2–3% of the patients (1, 5, 6). Unfortunately, a groin recurrence after IFL have a very high mortality rate, the prognoses after a negative SLN procedure is unclear; therefore very strict criteria with respect to tumour characteristics, preoperative and pathological assessment and surgical technique should be met to guarantee the safety of the SLN procedure and to minimize the number of false negative results and the risk of groin recurrence. Local recurrences of SCC of the vulva are reported in 20–46%(7). Many of these recurrences might be second primary tumours in a background of lichen sclerosis and differentiated vulvar intraepithelial neoplasia or high grade squamous cell intraepithelial lesion (HSIL) of the vulva rather than a real recurrence(8, 9). In patients with recurrent vulvar SCC, IFL is considered standard treatment for patients who previously did not undergo an IFL(10). So, in case of a local recurrence, only after bilateral IFL groin surgery is omitted. Since many of these patients are elderly and frail an alternative treatment other than IFL may be justified to avoid or reduce long term morbidity in this particular group of patients. In a retrospective analysis of it was shown that in a considerable number of patients groin surgery is not performed, in contrast with the guideline. In a retrospective study including 200 women with a macro invasive local recurrence the risk for groin metastases was 18%, and related to depth of invasion and tumour diameter. (Personal communication [name]¹). The lower percentage of groin lymph node metastases in case of a local recurrence compared to primary SCC is probably explained by earlier diagnosis due to standard follow-up.

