5.1.2 Preoperative definition of planned surgery

Prior to surgery the gynaecologic oncologist has to state what groin surgery should be done; ipsi or bilateral groin treatment and what treatment should be done in case the SLN is not visible, or not found during surgery. This decision relates to the previous groin treatment and whether or not the tumour crosses the midline. (See figures planned surgery). All SLN shown by imaging should be removed, also contralateral nodes in lateral tumours, and nodes in groins previously treated with IFL or radiotherapy, unless stated otherwise prior to surgery. In the current (standard) treatment protocol (www.oncoline.nl) groin surgery is not performed in local recurrent vulvar cancer after a previous IFL. Women should have an IFL in case of technical problems (SLN does not appear on the scintigraphy, or cannot be retrieved at surgery). Women that do not consent for a full IFL in case of technical problems (SLN does not appear on the scintigraphy, or cannot be retrieved at surgery), are more likely to experience groin recurrences (post-priory 17%). When women do not consent for IFL this should be noted prior to surgery.

Figures flow charts planned surgery see addendum 2.

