5.1.4 Surgical protocol

Treatment consists of wide local excision of the vulvar tumour or a vulvectomy in combination with SLN procedure. All groins with a SLN on imaging should be explored; also when previously IFL was performed at that site. When sentinel nodes in one or two groins cannot be identified an inguinofemoral lymphadenectomy at either one or two sides should be performed, depending on the location of the tumour and consent of the patient. (Figures 2, 3 and 4) When preoperative imaging showed any enlarged groin node (shortest axis > 8 mm) this node should be removed.

5.1.5 Histopathology:

Macroscopy: the number of lymph nodes received should be described, as well as the size and macroscopic aspects of the lymph nodes. The lymph node should be cut in 2-3 mm slices, perpendicular to the long axis and then all slices should be embedded (do not embed different lymph nodes in the same block).

Microscopy: one routine H/E section (four mu) should be cut of all blocks and two unstained sections (do not cut deep into the block). If the sections are tumour negative step sections, 3 levels/mm (one section per 500 micro meter), should be cut. For the three sections at each level, one is stained with H/E, one is to be used for immunohistochemistry (cytokeratin AE1/AE3), while one spare section is preserved in case of technical difficulties with the IHC (include the first level for IHC). Metastases are defined as clusters of tumour cells of any size detected on haematoxylin and eosin slides or at immunohistochemistry, or isolated tumour cells detected at immunohistochemistry. Anucleate keratin-positive structures are not considered positive. The diameter of the sentinel node metastasis and presence of extranodal growth will be recorded.

Pathologic ultra-staging will only be performed on sentinel nodes and not on non-sentinel nodes as identified in full lymphadenectomy specimens.

Reporting: number of sentinel nodes. Number of lymph nodes in lymphadenectomy specimen. Number of nodes with metastatic involvement. Size of lymph node metastasis. Extra nodal tumour growth.

5.1.6 Additional surgery:

In case of a positive SLN on histology a full IFL is advised. However, local protocol might advise postoperative radiotherapy under certain circumstances.

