5.1.8 Follow-up

During the first 24 months follow-up will be done three-monthly: with physical examination including inspection and palpation of the groins and of the vulva, inspection of the legs (lymph oedema) and notification of the number of erysipelas episodes.

At months 6, and 12, and in case of suspected groin nodes, an ultrasound scan of the groins is requested. When ultrasonography shows enlarged or suspect lymph nodes, a FNA will be performed.

After 24 months the follow-up will be done in accordance with local protocols.

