8.1.3 Other study parameters

Baseline data:

FIRST procedure: age at first procedure, localisation of tumour (medial / lateral), tumour size, depth of infiltration, LVSI, number of SLN right groin, number of SLN

left groin, IFL right site (number of lymph nodes), IFL left site (number of lymph nodes), previous radiotherapy, presence of LS or dysplasia, previous reconstructive surgery.

Interval between first surgical treatment and moment of relapse, guessed / estimated distance (cm) between original tumour and relapse, localisation of relapsed tumour, tumour size.

Intention to remove SLN ipsi- or bilateral, agreement on performing IFL in case SLN is not detected or retrieved.

Questionnaires

EQ-5D-5L. Standardized descriptive system of health-related quality of life states consisting of five dimensions (mobility, self-care, usual activities, pain/discomfort, anxiety/depression) each of which can take one of five responses. The responses record five levels of severity (no problems/some problems/ moderate problems/severe problems/extreme problems) within a particular EQ-5D dimension. Besides the descriptive system, a standard vertical 20 cm visual analogue scale (similar to a thermometer) for recording an individual's rating for their current health-related quality of life state is part of the EQ-5D. It was developed by the EuroQol Group. (14, 15)

Decisional Conflict Scale (DCS). This scale measures: 1) health-care consumers' uncertainty in making a health-related decision; 2) the factors contributing to the uncertainty; and 3) health-care consumers' perceived effective decision making. Internal consistency coefficients range from 0.78 to 0.92. (16) This questionnaire will only be used at baseline.

Decision Regret Scale (DRS). The DRS is a 5-item scale and a useful indicator of health care decision regret at a given point in time. Internal consistency is good (Cronbach's alpha = 0.81 to 0.92). This questionnaire will be used to evaluate patient's decision 1 year after surgery. (17)

GCLQ7 questionnaire: This is a short version of the Gynaecologic Cancer Lymphedema Questionnaire. This questionnaire will be used at baseline, 6 and 12 months. (18)

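### No preoperative clinical lymphoedema assessment is listed, so lymphoedema from earlier groin treatment may enter the 10.3 incidence and distort the SLN-versus-IFL comparison

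*Protocol*

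**What the plan says.** Section 10.3, under surgical complications, sets the outcome as "i.e., incidence of wound infections, wound breakdown, lymph oedema (see adverse effect Appendix 2) per patient and as absolute number". The results are to be read against each woman's earlier history and the groin operation she had, in everyone treated surgically, and the comparison is given as "comparing SLN treated groins with IFL treated groins". The section gives no rule for lymphoedema already present before the operation.

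The clinical recordings that the protocol names all come after surgery. Section 8.1.2 has the physician collect complications, lymphoedema among them, 6 weeks after each operation. Section 5.1.8 adds three-monthly visits for 24 months with "inspection of the legs (lymph oedema) and notification of the number of erysipelas episodes".

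The baseline list in 8.1.3 records earlier SLN and IFL by side and ends with "previous radiotherapy, presence of LS or dysplasia, previous reconstructive surgery". It has no lymphoedema item. A self-report lymphoedema questionnaire (GCLQ) is sent to all groups at baseline, 6 and 12 months (sections 3 and 8.1.3, Appendix 6).

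Earlier groin treatment is allowed. The Summary admits women with previous SLN, IFL and/or radiotherapy, and 4.3 excludes only certain combinations of IFL with radiotherapy. Section 5.1.4 states: "All groins with a SLN on imaging should be explored; also when previously IFL was performed at that site". Section 10.2 has an outcome specifically for SLNs found in previously treated groins, so the protocol expects such women.

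**The concern.** Incidence needs a starting state. A leg first inspected 6 weeks after the operation and found swollen may have been swollen before it, and the clinical data listed in the protocol cannot tell the two apart. The protocol's own background figures show that this is not a rare state: for lymphoedema and recurrent erysipelas respectively it cites "25.2% and 16.2% after inguinofemoral lymphadenectomy", against 1.9% and 0.4% after SLN.

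The error would probably be unequal between the compared groins. Section 5.1.2 says of standard care that "groin surgery is not performed in local recurrent vulvar cancer after a previous IFL", while the study explores a previously dissected groin when it shows an SLN. Groins with an earlier IFL should therefore collect on the SLN side.

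At stake is secondary objective 2, the short- and long-term morbidity of the SLN procedure. Lower morbidity is also the reason the Summary gives for accepting an additional 5% failure rate. A study meant to show how much morbidity SLN spares could understate it.

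**Working it through.** The protocol states no figure for this outcome, so there is none to reproduce. The check has two parts.

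**1. What is known about a leg, and when**

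| Time | Source | Lymphoedema information |
|---|---|---|
| Before surgery | 8.1.3 baseline list | None. Earlier groin treatment only |
| Before surgery | GCLQ (8.1.3, Appendix 6) | Yes/no self-report, no side, no grade |
| 6 weeks | 8.1.2 | Physician-recorded complication |
| 3 to 24 months, every 3 months | 5.1.8 | Leg inspection by the clinician |
| 6 and 12 months | GCLQ | As at baseline |

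The physician-recorded outcome has no preoperative value on the same scale. The CTCAE grades in Appendix 3 could supply one, but no section asks for them before surgery.

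**2. How large the mixture could be (illustration only)**

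Inputs from section 1 (Introduction): lymphoedema 25.2% after IFL and 1.9% after SLN, both from the primary setting.

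Assumptions: a share f of SLN women had an earlier IFL (the protocol gives no share; 10% to 40% is used); the 25.2% persists until the recurrence; women without an earlier IFL bring none.

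- Existing cases: E = f × 25.2%
- New cases among the rest: N = (1 − E) × 1.9%
- Recorded after surgery if the two are not separated: R = E + N

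| f | E | N | R | E ÷ 1.9% |
|---|---|---|---|---|
| 10% | 2.5% | 1.9% | 4.4% | 1.3 |
| 20% | 5.0% | 1.8% | 6.8% | 2.7 |
| 40% | 10.1% | 1.7% | 11.8% | 5.3 |

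Per 150 women (a convenient denominator) the existing cases would number about 3.8, 7.6 and 15.1, against 150 × 1.9% = 2.9 expected new ones. Existing cases equal the expected new ones at f = 1.9 ÷ 25.2 = 7.5%.

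If instead every woman without an earlier IFL had an earlier SLN and carried its 1.9%, E = f × 25.2% + (1 − f) × 1.9% gives 4.2%, 6.6% and 11.2%.

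The calculation counts women, whereas the 10.3 comparison is between groins. It shows the order of size and does not predict the result.

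**The case against.** A reader might infer that the protocol counts existing lymphoedema as a complication of SLN. No section says so. Section 10.3 speaks of incidence, which ordinarily means new cases, and relates the results to previous history. Appendix 4 lists the case report forms by title only, so a preoperative lymphoedema item cannot be ruled out. This part of the objection stands: the point is that existing cases may be counted, not that they are.

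A reader might also infer that earlier erysipelas is counted. The documents do not support that. Section 5.1.8 notes episodes at visits after surgery. Those are new events, and erysipelas is not named in the 10.3 sentence. Lasting susceptibility in a previously dissected leg is confounding by earlier treatment, a different matter.

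The GCLQ does give a baseline and a change per woman. However, it is a set of yes/no items without side or grade, it ends at 12 months while leg inspection runs to 24, and nothing links it to the physician's record. It cannot correct a comparison of groins.

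Relating results to previous history helps more. Earlier IFL is recorded by side, so groins without earlier treatment can be compared cleanly. Within previously treated groins, old and new lymphoedema remain mixed.

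A statistical analysis plan may well define incident lymphoedema. It cannot supply a preoperative grade that was never recorded.

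Finally, the outcome is not primary, neither the sample size nor the stopping rule uses it, and the likely bias runs against SLN. That limits the consequence but does not remove it.

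**Conclusion.** The concern holds for lymphoedema. The protocol lists no preoperative clinical assessment and starts clinical recording 6 weeks after surgery in a population that includes women with earlier IFL or groin radiotherapy. Existing lymphoedema may therefore enter the 10.3 incidence, probably more on the SLN side. The direction is likely but not certain, because IFL-treated groins can also carry lymphoedema from earlier radiotherapy or SLN.

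The problem is confined to previously treated groins. Its size is unknown. In the illustration, about 2.5 to 10 percentage points of existing cases sit beside 1.9% of new ones. This rests on an assumed 10% to 40% share with earlier IFL and on the primary-setting rate persisting. The gap deserves correction because it is cheap to close before surgery and hard to close afterwards.

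**What to change.** - **8.1.3 and a preoperative form:** add CTCAE lymphoedema grade per leg, for example on Form D1. Appendix 4 has Forms C to H returned after surgery, so the entry should carry the date of the preoperative examination, or sit on Form A or B, which are sent before treatment.
- **10.3:** define incident lymphoedema as new, or worsened over the preoperative grade, in the same leg. Report existing cases separately. Correct the cross-reference at the same time: 10.3 points to Appendix 2 and 8.1.2 to Appendix 1, while the CTCAE criteria are in Appendix 3.
- **Optional:** record erysipelas history before surgery as a descriptive covariate.

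The cost is one or two extra baseline items at an examination that already takes place. For women already enrolled, preoperative status would have to be retrieved from charts and may be incomplete; those values should be marked as retrospective.

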Nature and extent of the burden and risks associated with participation, benefit and group relatedness: In this study, similar to the current routine, preoperative imaging of chest, abdomen and groins is performed. The patient is informed about the standard procedure and about the option of a SLN procedure. She and her treating gynaecologist decide on the preferred treatment. Prior to surgery the planned surgical procedure is recorded, including patients' consent for IFL in case the SLN procedure fails. The surgical procedure (SLN procedure) will be less extensive compared to routine IFL, with less unfavourable short and long term effects, such as infections and lymph oedema. In case of groin metastases detected in the SLN procedure further treatment is warranted, either by surgery (uni or bilateral IFL) and/or by radiotherapy. At follow up participants will undergo (non-invasive) ultrasonography studies of the groin at 6 and 12 months. Participants will be asked to fill in additional questionnaires at baseline, 6 and 12 months. In case of a groin recurrence (due to failed SLN procedure) further treatment is warranted, probably resulting in a poorer prognosis with a high mortality rate (probably 80-90%). Currently, robust data on the occurrence of groin recurrence after either SLN biopsy or IFL for recurrent vulvar cancer is lacking. Given the lower morbidity and less short and long term side effects of the SLN procedure compared to IFL an additional 5% failure rate is considered acceptable.

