4.4 Sample size calculation

Approximately 18% of women will have groin metastases at the moment of their first vulvar cancer recurrence. Of these, approximately 20% will be detected prior to surgery (based on imaging and FNA) and these women will not be offered a SLN procedure, but advised to undergo an IFL(s). They will be asked for the observational arm of the non SLN cohort. (See figure 2)

The remaining patients will be informed about the study, they can decide on standard IFL (group A) or refuse any surgery of the groin(s) (group C) In 75% of cases that undergo SLN (group B) it will be possible to retrieve the SLN. In approximately 14,5% of women undergoing a SLN procedure a tumour positive node will be present. It is not expected that the change of a successful SLN procedure relates to the presence or absence of a positive groin node. We expect to find a positive SLN in 11% of cases undergoing a SLN procedure, a negative SLN in 64%, and an unsuccessful procedure in 25%. This corresponds to respectively 10.5%, 61.8% and 24.1% of all included patients.

Percentage failure of SLN or IFL is known for neither procedure in the recurrent setting. In the primary setting groin recurrence after negative IFL and after negative SLN are both about 3%.

Sample size for V2SLN is calculated based on a conservatively estimated groin recurrence rate of 3%, with a maximum additional groin failure rate of SLN in local recurrent vulvar SCC of 5%. The sample size, considering an alpha of 0.10 and a beta of 0.20, is then calculated to be 150 patients with a first vulvar cancer recurrence undergoing a SLN procedure (group B) and a negative SLN (Figure 2) So, we expect that approximately 243 women with a 1st recurrence of vulvar cancer should be included in the study. Stopping rules with dynamic boundaries were constructed to guarantee the safety of the study by continuously monitoring the number of groin recurrences. See Appendix 1 for a detailed description of these stopping rules.

[figure not shown]

Figure 2 Flow diagram of calculation of sample size

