Appendix 4: Procedures and forms data collection.

Patient's registration will only be accepted from authorized investigators.

Patients should sign informed consent prior to registry.

Overview of the forms and additional documents to be collected:

Form	Name	When	Additional documents
A	ELIGIBILITY FORM (A)	Registration	
B	DECISION ON TREATMENT FORM (B)	Registration	
C	PRIMARY TUMOUR & LYMPH NODES FORM (C)		Photograph when (still) available
D1	CURRENT TUMOUR & LYMPH NODES FORM (D1)		Photograph with ruler
D2	PRE OPERATIVE IMAGING FORM-ULTRASOUND- (D2)		Copy of imaging report CoIR)
D3	PRE OPERATIVE IMAGING FORM-CT- (D3)		CoIR
D4	PREOPERATIVE IMAGING FORM –MRI- (D4)		CoIR
E	TUMOUR SURGERY TREATMENT FORM (E)		Surgical notes
F	SENTINEL NODES SURGERY FORM (F)		Surgical notes
G	POSTOPERATIVE PERIOD FORM (G)		
H	PATHOLOGY REPORT FORM (H)	After surgery	Original pathology report
J	ADDITIONAL TREATMENT FORM (J)		
K	FOLLOW UP FORM 3 MONTHS AFTER COMPLETION OF TREATMENT(k)		
L	FOLLOW UP FORM 6 MONTHS AFTER COMPLETION OF TREATMENT: clinical assessment (L)		
M	FOLLOW UP FORM 6 MONTHS AFTER COMPLETION OF TREATMENT: Ultrasound scan(M)	6m	CoIR
N	FOLLOW UP FORM 9 MONTHS AFTER COMPLETION OF TREATMENT(N)		
O	FOLLOW UP FORM 12 MONTH AFTER COMPLETION OF TREATMENT clinical assessment(O)		
P	FOLLOW UP FORM 12 MONTHS AFTER COMPLETION OF TREATMENT ultrasound scan (P)	12 m	CoIR

Q	FOLLOW UP FORM 15 MONTHS AFTER COMPLETION OF TREATMENT(Q)		
R	FOLLOW UP FORM 18 MONTHS AFTER COMPLETION OF TREATMENT(R)		
S	FOLLOW UP FORM 21 MONTHS AFTER COMPLETION OF TREATMENT(S)		
T	FOLLOW UP FORM 24 MONTHS AFTER COMPLETION OF TREATMENT(T)	24 m	

Patients must be registered prior to surgery. A patient can be registered after verification of eligibility: Form A (eligibility form).

At registration, before surgery Form B (planned surgery) should be completed to minimize bias.

At the end of the registration procedure, a number will be allocated to the patient (patient sequential study number) send by the study secretariat by fax or email.

The study identification number attributed to the patient at the end of the registration procedure identifies the patient and must be reported on all case forms.

After surgery additional treatment is given, or the observational study starts.

Patient data will be collected in standard case report forms with NCR (non-carbon required) paper or through an electronic database.

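### Section 10.3 compares complications only by groin surgery performed, which describes each procedure but not the effect of replacing IFL by an SLN strategy

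*Protocol*

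**What the plan says.** - **Grouping.** Protocol section 10.3 (Surgical complications) covers wound infection, wound breakdown and lymphoedema. It relates them to "history and groin surgery performed, including all surgically treated patients (Groups non SLN cohort and A – C"), and the contrast is "comparing SLN treated groins with IFL treated groins".
- **Failed SLN.** Section 4.4 states: "In 75% of cases that undergo SLN (group B) it will be possible to retrieve the SLN". Sections 5.1.2 and 5.1.4 call for IFL when the node is not seen or not retrieved, subject to tumour location and the woman's consent.
- **Positive SLN.** Section 4.4 expects a positive node in 11% of women undergoing the procedure, "a negative SLN in 64%, and an unsuccessful procedure in 25" per cent. Section 5.1.6 says: "In case of a positive SLN on histology a full IFL is advised". It allows that local protocol may advise radiotherapy.
- **Purpose.** The primary objective (section 2) concerns replacing complete IFL by SLN. Secondary objective 2 concerns morbidity associated with the SLN procedure. The Summary bases its tolerance for extra groin failures on morbidity: "Given the lower morbidity and less short and long term side effects of the SLN procedure compared to IFL an additional 5% failure rate" is called acceptable.
- **Data.** Appendix 4 says: "At registration, before surgery Form B (planned surgery) should be completed to minimize bias". Section 8.1.2 collects complications six weeks after every operation. Section 5.1.8 has the legs inspected for lymphoedema every three months to 24 months.

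**The concern.** Before surgery a woman chooses between IFL and a strategy that starts with SLN and may still end in IFL. Section 10.3 instead sorts groins by what was done, and part of that is decided after the SLN has failed or proved positive. The morbidity of those later IFLs is nowhere attributed to the SLN strategy or separated from the IFLs of women who chose IFL. Section 10.3 also gives no rule for a groin that had both procedures.

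At stake is what the trial can say about morbidity. The protocol accepts up to 5 percentage points more groin failure because SLN is expected to cause less harm. A contrast limited to procedures leaves out the harm that the SLN route adds through rescue and completion surgery, so it cannot by itself inform that trade-off for a woman deciding beforehand.

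**Working it through.** **Inputs.** Section 4.4: 18% groin metastases, 20% of these found before surgery, 75% retrieval, 14.5% node-positive among women undergoing SLN, 150 negative SLNs needed. Section 1 (primary disease): lymphoedema 1.9% after SLN and 25.2% after IFL. The document gives no rate for groins that had both procedures and no expected share for group B2.

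**Step 1: reproduce the protocol's flow.**
- Positive: 0.75 × 0.145 = 10.9% (stated 11%). Negative: 0.75 × 0.855 = 64.1% (stated 64%). Unsuccessful: 25%.
- Share of included women reaching this point: 1 − 0.18 × 0.20 = 0.964. Multiplying gives 10.5%, 61.8% and 24.1%, as stated.
- 150 / 0.618 = 242.7, so 243, as stated.

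**Step 2: share s of group B going on to IFL.** The maximum is 25% + 10.9% = 35.9%. It is an upper bound: B2 women decline rescue IFL, positive women may have radiotherapy instead, and Appendix 2 (flowchart A) gives no further treatment after some contralateral failures.

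**Step 3: strategy rate.** R = s × 25.2 + (1 − s) × 1.9. The strategy benefit is 25.2 − R. The procedure contrast is 25.2 − 1.9 = 23.3 points. Women without IFL are given the SLN rate; women with SLN and then IFL are given the IFL rate.

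| Who has IFL | s | R | Benefit (points) | 23.3 / benefit |
|---|---|---|---|---|
| All failures and all positives | 35.9% | 10.3% | 14.9 | 1.56 |
| All failures, no positives | 25.0% | 7.7% | 17.5 | 1.33 |
| Half of each | 17.9% | 6.1% | 19.1 | 1.22 |
| All positives, no failures | 10.9% | 4.4% | 20.8 | 1.12 |

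The ratio equals 1 / (1 − s), so it depends only on the share going on to IFL and not on the lymphoedema rates.

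**Step 4: who makes up the IFL side.** With 243 included, 243 × 0.964 ≈ 234 undergo SLN. About 59 fail and 25 are positive, so up to 84 women reach IFL through SLN. The flow leaves no room for group A. The only other IFL women are 243 × 0.036 ≈ 9 with metastases found beforehand, so 84 / 93 ≈ 91% of IFL women come through SLN. If 20% of eligible women chose IFL (an assumption), the share is 0.8 × 0.359 / (0.8 × 0.359 + 0.2 + 0.036/0.964) ≈ 55%. At 50% it is about 25%. These shares also use the maximum s.

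**The case against.** The strongest reply is that this is a different question, not a bias. Secondary objective 2 asks about the morbidity of the SLN procedure, and a comparison by procedure answers it. In the calculation neither rate is distorted: SLN stays at 1.9% and IFL at 25.2%, and 1.56 is the ratio of two estimands. That stands. A reader might infer that section 10.3 as planned overstates the benefit of SLN. The text does not support this, because it nowhere says the contrast will be reported as a strategy effect.

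A reader might also infer that groins with both procedures will be counted as IFL. That is a natural reading of a grouping by surgery performed, but it is not stated, and such detail may sit in an SAP that is not shown.

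The extra 5% failure applies to women with a negative SLN (sections 4.4 and 10.1), for whom morbidity after SLN alone is the matching benefit. This is fair for those women. It does not help at the moment of choice, when the SLN result is unknown.

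Other parts of the plan come closer to strategy. Complication incidence is also given per patient, quality of life is compared between standard and study-arm patients (section 10.2), and the lymphoedema questionnaire goes to every group (Appendix 6). None of these states a complication comparison by chosen strategy.

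The figures have limits. The rates come from primary disease and are applied per woman, whereas the planned contrast is per groin. The retrospective series in section 1 had 77% success per patient but 84% per groin.

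Finally, group A against group B cannot simply become the main comparison. Women choose their own group, the 243 allows for no group A, and section 10.2 makes even the IFL recurrence rate conditional on enough women choosing IFL. This also stands and shapes the fix.

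**Conclusion.** The point holds in a limited form. Section 10.3 gives a legitimate procedure-level description but no complication analysis that answers the replacement question in the primary objective or the trade-off in the Summary. If the contrast were read as a strategy effect it would favour SLN. On the protocol's lymphoedema rates, the benefit would be at least 14.9 points instead of 23.3 (ratio up to 1.56), and about 19.1 (ratio about 1.22) if half the failed and half the positive women had no IFL.

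This rests on primary-setting rates carrying over and on SLN followed by IFL having the same rate as IFL alone. If two operations cause more harm than one, the 14.9 would not be a floor. The 36% should not be read as the expected chance of IFL; it is the maximum implied by section 4.4.

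This is a descriptive parameter in a non-randomised study. The primary endpoint, the 150 women with a negative SLN and the stopping rule are untouched. It is a cheap improvement and not a flaw in the main design.

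**What to change.** In section 10.3, under Surgical complications:

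1. Add a per-woman analysis by the strategy recorded before surgery on Form B. Report all of group B (B1 and B2), including women who convert to IFL or are completed with IFL or radiotherapy, and cumulate complications over all groin operations and the three-monthly follow-up (Forms E to T).
2. Set this descriptively beside group A as far as numbers allow, and state that the groups are self-selected.
3. Keep the groin-level comparison by surgery performed, labelled as a description of procedures, with SLN-then-IFL groins as a separate class.
4. Leave Technical challenges by procedure. Vein injury, bleeding and time to retrieve the node belong to the operation itself.

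**Cost.** One paragraph of text and one more table, with no new data. The stated benefit of SLN becomes less favourable, and the comparison of A with B is non-randomised and may be imprecise because group A may be small.
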